#### **6.4.9. Other procedures**

- Vasculitis activity score (Birmingham vasculitis score). This score includes the following items: (1) general, (2) cutaneous, (3) mucous membranes/eyes, (4) ENT, (5) chest, (6) cardiovascular, (7) Abdominal, (7) renal, (8) Nervous system, (9) other. This score is based on patient self-report, medical history, physical examination

serum creatinine, urine creatinine and urinalysis (proteinuria, hematuria). Appendix 6. Only for subjects with vasculitis.

- Sicca syndrome evaluation. This will be assessed by PI in all visits based on patient self-report and physical examination to assess amount of saliva and tears. On screening and post treatment week 24 visits [name] will perform a Schirmer test to assess xerophthalmia and will measure saliva from Stensen's duct to assess xerostomia (39,40). Only for subjects with sicca syndrome.
- ACR20-70 score. This score includes the assessment following items: 1) at swollen joint counts, 2) tender joint counts, 3) patient-assessed global disease activity (i.e. by VAS), 4) evaluator-assessed global disease activity (i.e. by VAS), 5) patient pain assessment (i.e. by VAS), 6) functional disability (i.e. by HAQ), 7) acute phase response (ESR or PCR). A 20 and 70 percent response (ACR20-70) represents improvement of at least 20 or 70 percent (41). Only for subjects with Rheumatoid arthritis.
- Glomerulonephritis evaluation. This will be assessed by 1) the presence of hematuria, proteinuria and red cell casts by urinalysis, 2) quantification of proteinuria on a 24 hour collection or as the protein/creatinine ratio of a spot sample of urine and 3) concomitant renal insufficiency is defined as serum creatinine >2.0mg/dL. Only for subjects with glomerulonephritis.
- Neuropathy evaluation will be evaluated by complete and detailed physical examination performed by [name] in every visit. For those subjects with neuropathy associated cryoglobulinemia, on screen and post-treatment week 24 visits this will be performed by [name], and neuropathy will be corroborated by electrophysiologic testing.
- Complement studies:
  - MBL, Generation attack complex (C5-9), Rheumatoid factor, IgM, C3, C4 and C4a analysis will be performed through the Core Laboratory at Mount Sinai Health Care System.
  - C1q, C1q binding assays and gC1qR will be performed at our clinical immunology laboratory, and in the Laboratory of [name] (State University of New York, Stony Brook).
- Cryoprecipitation characterization studies:

- Analysis of MC and of cross-reactive idiotypes (CRI) will be separated and frozen to be analyzed on a later date at the Flow Cytometry Laboratory at Mount Sinai Health Care System.
- Regression of clonality/lymphoproliferation and FACS analysis, this includes:
  - B-cell surface antigens, kappa/lambda light chain on B cells, CLL lymphoma panel and CD81, that will be performed at the Flow Cytometry Shared Resource Core Facility and at our Clinical Immunology Laboratory
  - Isolate PBMCs for CyTOF analysis to investigate the patients mononuclear cellular immunity profile during and after DAA treatment cell populations to be analyzed by CyTOF. Samples will be frozen and analysis on a later date.
- HCV core ELISA: this includes:
  - Compartmentalization of viral RNA and core antigen between cryoprecipitable and non-cryoprecipitable immune complexes will be performed with support from our institutional Human Immune Monitoring Core Facility.
  - HRP conjugated HCV core Ag antibodies will be obtained commercially with assays to be performed with support from our Human Immune Monitoring Core Facility.
  - FITC-conjugated secondary antibodies will be obtained commercially and tested for optimal resolution in our institutional Flow Cytometry Shared Resource Core Facility.

## **7. TOXICITY MANAGEMENT**

### **7.1. Dose Modification Due to Toxicity**

There is no option for dose reduction or modification of LDV/SOF or SOF/VEL.

### **7.2. Toxicity Stopping Criteria**

Administration of all study medication(s) may be discontinued in the event of a clinical or laboratory event. The PI must be consulted prior to dose discontinuation of LDV/SOF or SOF/VEL unless the investigator believes that immediate action is warranted to ensure the continued safety of the subject. Subjects who meet any of the following laboratory criteria must stop all study medication(s):

- Elevation of ALT and/or AST >5x Baseline/Day 1 or nadir, confirmed by immediate repeat testing
- Abnormal elevation of ALT >3x Baseline/Day 1 and total bilirubin >2 x ULN, confirmed by immediate repeat testing
- Elevation of ALT >15 x ULN, confirmed by immediate repeat testing
- Any Grade 3 or greater rash associated with constitutional symptoms
- Any Grade 4 adverse event or laboratory abnormality assessed (and confirmed by immediate repeat testing) as related to LDV/SOF or to SOF/VEL.
- Any unacceptable side effect of the drug (i.e. hypersensitivity reaction, abnormal Liver function tests; gastrointestinal side effects) in the judgment of the Investigator compromises the ability to continue study specific procedures or is considered to not be in the subject's best interest.
- A paradoxical effect on the disease manifestations (i.e. increased or systemic vasculitis, renal failure)

## **8. ADVERSE EVENTS MANAGEMENT**

### **8.1. Definitions of Adverse Events, Adverse Reactions, and Serious Adverse Events**

An adverse event (AE) is any untoward medical occurrence in a clinical study subject administered a medicinal product, which does not necessarily have a causal relationship with the treatment. An AE can therefore be any unfavorable and/or unintended sign, symptom, or disease temporally associated with the use of a medicinal product, whether or not considered related to the medicinal product. AEs may also include pre- or post-treatment complications that occur as a result of protocol specified procedures, lack of efficacy, overdose, drug abuse/misuse reports, or occupational exposure. Pre-existing events that increase in severity or change in nature during or as a consequence of participation in the clinical study will also be considered AEs.

An AE does not include the following:

- Medical or surgical procedures such as surgery, endoscopy, tooth extraction, and transfusion. The condition that led to the procedure may be an adverse event and must be reported.
- Pre-existing diseases, conditions, or laboratory abnormalities present or detected before the screening visit that do not worsen.
- Situations where an untoward medical occurrence has not occurred (e.g., hospitalization for elective surgery, social and/or convenience admissions).
- Overdose without clinical sequelae.
- Any medical condition or clinically significant laboratory abnormality with an onset date before the consent form is signed and not related to a protocol-associated procedure is not an AE. It is considered to be pre-existing and should be documented on the medical history CRF.

#### **8.1.1. Classification of Adverse Events**

##### **8.1.1.1. Serious Adverse Events**

A serious adverse event (SAE) is defined as an event that, at any dose, results in the following:

- Death

- Life-threatening (Note: The term “life-threatening” in the definition of “serious” refers to an event in which the subject was at risk of death at the time of the event; it does not refer to an event that hypothetically might have caused death if it were more severe.)
- In-patient hospitalization or prolongation of existing hospitalization
- Persistent or significant disability/incapacity
- A congenital anomaly/birth defect
- A medically important event or reaction: such events may not be immediately life-threatening or result in death or hospitalization but may jeopardize the subject or may require intervention to prevent one of the other outcomes constituting SAEs. Medical and scientific judgment must be exercised to determine whether such an event is a reportable under expedited reporting rules. Examples of medically important events include intensive treatment in an emergency room or at home for allergic bronchospasm; blood dyscrasias or convulsions that do not result in hospitalization; and development of drug dependency or drug abuse. For the avoidance of doubt, infections resulting from contaminated medicinal product will be considered a medically important event and subject to expedited reporting requirements.

#### **8.1.2. Clinical Laboratory Abnormalities and Other Abnormal Assessments as Adverse Events or Serious Adverse Events**

Laboratory abnormalities without clinical significance are not recorded as AEs or SAEs. However, laboratory abnormalities (e.g., clinical chemistry, hematology, and urinalysis) that require medical or surgical intervention or lead to study drug interruption, modification, or discontinuation must be recorded as an AE, as well as an SAE, if applicable. In addition, laboratory or other abnormal assessments (e.g., electrocardiogram, x-rays, vital signs) that are associated with signs and/or symptoms must be recorded as an AE or SAE if they meet the definition of an AE or SAE as described. If the laboratory abnormality is part of a syndrome, we will record the syndrome or diagnosis (e.g., anemia), not the laboratory result (i.e., decreased hemoglobin).

#### **8.2. Assessment of Adverse Events and Serious Adverse Events**

The investigator or qualified sub-investigator is responsible for assessing AEs and SAEs for causality and severity, and for final review and confirmation of accuracy of event information and assessments.

#### **8.2.1.1. Assessment of Causality for Study Drugs and Procedures**

The investigator or qualified sub-investigator is responsible for assessing the relationship to therapy using clinical judgment and the following considerations:

- No: Evidence exists that the adverse event has an etiology other than the drug. For SAEs, an alternative causality must be provided (e.g., pre-existing condition, underlying disease, intercurrent illness, or concomitant medication).
- Yes: There is reasonable possibility that the event may have been caused by the investigational medicinal product.

It should be emphasized that ineffective treatment should not be considered as causally related in the context of adverse event reporting.

The relationship to study procedures (e.g., invasive procedures such as venipuncture or biopsy) should be assessed using the following considerations:

- No: Evidence exists that the adverse event has an etiology other than the study procedure.
- Yes: The adverse event occurred as a result of protocol procedures (eg., venipuncture)

#### **8.2.1.2. Assessment of Severity**

The severity grading of AEs will be assessed as Grade 1, 2, 3, or 4 using the GSI Grading Scale for Severity of Adverse Events and Laboratory Abnormalities (Appendix 2). For AEs associated with laboratory abnormalities, the event should be graded on the basis of the clinical severity in the context of the underlying conditions; this may or may not be in agreement with the grading of the laboratory abnormality.

### **8.3. Investigator Requirements and Instructions for Reporting Adverse Events and Serious Adverse Events**

Requirements for collection prior to study drug initiation:

After informed consent, but prior to initiation of study medication, the following types of events should be reported on the case report form (CRF/eCRF): all SAEs and adverse events related to protocol-mandated procedures.

#### Adverse Events

Following initiation of study medication, all AEs, regardless of cause or relationship, until 4 weeks after last administration of study drug must be collected and reported on the CRF/eCRF database as instructed.

All AEs should be followed up until resolution or until the adverse event is stable, if possible.

#### Serious Adverse Events

All SAEs, regardless of cause or relationship, that occur after the subject first consents to participate in the study (i.e., signing the informed consent) and throughout the duration of the study, including the protocol-required post treatment follow-up period, will be reported to the CRF/eCRF database and to the FDA. This also includes any SAEs resulting from protocol-associated procedures performed after informed consent is signed.

Any SAEs and deaths that occur after the post treatment visit, regardless of causality, will also be reported.

Investigators are not obligated to actively seek SAEs after the protocol-defined follow up period. However, if the investigator learns of any SAEs that occur after study participation has concluded and the event is deemed relevant to the use of study drug, this will be promptly documented, and the event reported to the FDA.

- All AEs and SAEs will be recorded in the CRF/eCRF database within the timelines outlined in the CRF/eCRF completion guideline and will be reported within 24 hours. SAEs will be reported accordingly to FDA guidelines. As soon as it is possible to do so, any SAE reported via paper will be transcribed into the eCRF Database according to instructions in the eCRF completion guidelines.
- For fatal or life-threatening events, copies of hospital reports, autopsy reports, and other documents will also be submitted by e-mail or fax when requested and applicable. Transmission of such documents should occur without personal subject identification, maintaining the traceability of a document to the subject identifiers.
- Additional information may be requested to ensure the timely completion of accurate safety reports.

- Any medications necessary for treatment of the SAE will be recorded onto the concomitant medication section of the subject's CRF/eCRF, and the event description section of the SAE form.
- The investigator will notify the IRB of SUSAR reports as soon as practical, where this is required by local regulatory agencies, and in accordance with the local institutional policy.

#### **8.4. Special Situations Reports**

##### **8.4.1.1. Definitions of Special Situations**

Special situation reports include all reports of medication error, abuse, misuse, overdose, reports of adverse events associated with product complaints, and pregnancy reports regardless of an associated AE.

- Medication error is any unintentional error in the prescribing, dispensing, or administration of a medicinal product while in the control of the health care provider, subject, or consumer.
- Abuse is defined as persistent or sporadic intentional excessive use of a medicinal product by a subject.
- Misuse is defined as any intentional and inappropriate use of a medicinal product that is not in accordance with the protocol instructions or the local prescribing information.
- An overdose is defined as an accidental or intentional administration of a quantity of a medicinal product given per administration or cumulatively which is above the maximum recommended dose as per protocol or in the product labeling (as it applies to the daily dose of the subject in question). In cases of a discrepancy in drug accountability, overdose will be established only when it is clear that the subject has taken the excess dose(s). Overdose cannot be established when the subject is unable to account for the discrepancy, except in cases in which the investigator has reason to suspect that the subject has taken additional dose(s).
  - No specific antidote is available for overdose with Harvoni® or Epclusa®. If overdose occurs the patient must be monitored for evidence of toxicity. Treatment of overdose with HARVONI® or Epclusa® consists of general supportive measures including monitoring of vital signs as well as observation

of the clinical status of the patient. Hemodialysis is unlikely to result in significant removal of ledipasvir since ledipasvir is highly bound to plasma protein. Hemodialysis can efficiently remove the predominant circulating metabolite of sofosbuvir, GS-331007, with an extraction ratio of 53%. Hemodialysis is unlikely to result in significant removal of velpatasvir since velpatasvir is highly bound to plasma protein.

- Product complaint is defined as complaints arising from potential deviations in the manufacture, packaging, or distribution of the medicinal product.

#### **8.4.1.2. Instructions for Reporting Special Situations**

##### **8.4.1.2.1. Instructions for Reporting Pregnancies**

The investigator will report pregnancies in female study subjects that are identified after initiation of study medication and throughout the study, including the post study drug follow-up period.

Pregnancy itself is not considered an AE, nor is an induced elective abortion to terminate a pregnancy without medical reason.

Any premature termination of pregnancy (e.g., a spontaneous abortion, an induced therapeutic abortion due to complications or other medical reasons) will be reported within 24 hours as an SAE. The underlying medical reason for this procedure will be recorded as the AE term.

A spontaneous abortion is always considered to be an SAE and will be reported as described above. Furthermore, any SAE occurring as an adverse pregnancy outcome post study will be reported to the FDA.

The subject should receive appropriate monitoring and care until the conclusion of the pregnancy. The outcome will be reported to the FDA using the pregnancy outcome report form. If the end of the pregnancy occurs after the study has been completed, the outcome will be reported directly to the FDA.

Pregnancies of female partners of male study subjects exposed to study drugs will also be reported, and relevant information submitted to the FDA using the pregnancy and pregnancy outcome forms within 24 hours. Monitoring of the subject will continue until the conclusion of the pregnancy. If the end of the pregnancy occurs after the study has been completed, the outcome will be reported directly to the FDA,

Refer to Appendix 4 for Pregnancy Precautions, Definition for Female of Childbearing Potential, and Contraceptive Requirements.

Any inappropriate use of concomitant medications prohibited by this protocol should not be reported as “misuse,” but may be more appropriately documented as a protocol deviation.

### **8.5. Warnings and Precautions**

Refer to HARVONI® (Ledipasvir/sofosbuvir) package insert for additional information (Appendix 5b).

Refer to Epclusa® (Sofosbuvir/Velpatasvir) package insert for additional information (Appendix 5b).

## **9. STATISTICAL CONSIDERATIONS**

This is a pilot study in which 10 patients will be enrolled to explore the efficacy of all-oral anti-viral therapy for symptomatic hepatitis C virus infection-related cryoglobulinemia.

With 10 patients in the study we will be able to estimate the rate of patients who obtain an SVR with a margin of error of approximately 15%.

We will use frequency table and 95% confidence interval to describe the rate of SVR in the total sample and the two subgroups of interest.

Results will be compared to previous published studies (28), as well as unpublished experience, that have delineated the natural history of type 2 cryoglobulinemia, and the response to immunomodulatory therapies, including IFN/Peg-IFN, Ribavirin and Rituximab (27).

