### **Objectives:**

The **primary objectives** of this study are:

- To assess the efficacy of new direct acting oral antivirals: LDV/SOF FDC (Harvoni®) or SOF/VEL FDC (Epclusa®) in patients with chronic HCV infection and MC, measuring the proportion of subjects who attain SVR at 4 and 24 weeks after cessation of treatment.
- To assess efficacy of new direct acting oral antivirals: LDV/SOF FDC (Harvoni®) or SOF/VEL FDC (Epclusa®) in patients with mixed cryoglobulinemia (MC) secondary to chronic HCV infection:

- A complete response is defined as disappearance of arthropathy or kidney involvement, and/or purpura, and >50% reduction in IgM-RF and cryocrit.
- A partial response is a 10-50% reduction in cryocrit and one (but not all) clinical and laboratory signs of systemic vasculitis.

The **secondary objectives** of this study are:

- To assess immunological response of MC to new direct acting oral antivirals: LDV/SOF (Harvoni®) or SOF/VEL FDC (Epclusa®) treatment measuring:
  - FACS/CyTOF analysis of PBMC to determine the effect of DAA treatment on cell-surface markers or MC
  - analysis of isolated mixed cryoglobulins for localization of viral RNA, the presence of HCV core antigen, C1q protein, C1q binding activity and soluble gC1qR.
  - accumulate kinetic data to address the issues of (a) redistribution of viral RNA and core protein between cryoprecipitable and noncryoprecipitable immune complexes with treatment (27) (b) persistence of cryoglobulins and cryoglobulinemic vasculitis following apparent clearance of virus (13,14,28); and (c) persistence of virus in PBMC or cryoprecipitates following apparent systemic clearance (i.e. occult infection) (29).
- To assess safety and tolerability of new direct acting oral antivirals: LDV/SOF FDC (Harvoni®) or SOF/VEL FDC (Epclusa®) in patients with chronic HCV infection and MC.

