**Statistical Methods:**

This is a pilot study in which 10 patients will be enrolled to explore the efficacy of all-oral anti-viral therapy for symptomatic hepatitis C virus infection-related cryoglobulinemia.

With 10 patients in the study we will be able to estimate the rate of patients who obtain an SVR with a margin of error of approximately 15%.

We will use frequency table and 95% confidence interval to describe the rate of SVR in the total sample and the two subgroups of interest.

Results will be compared to previous published studies (28), as well as unpublished experience, that have delineated the natural history of type 2 cryoglobulinemia, and the response to immunomodulatory therapies, including IFN/Peg-IFN, Ribavirin and Rituximab (27).

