manifestations of disease. However, the use of first generation direct-acting antiviral agents (Telaprevir® and Boceprevir® linear NS3/4A protease inhibitors) was limited by frequent escape mutants, efficacy restricted to genotype-1, need to retain protocols including PegIFN and ribavirin, potential for significant drug interactions, and serious side effects. In a trial of combination therapy including Telaprevir® for 13 patients with MC, all had significant AEs, including asthenia (92%), anemia (84%), neutropenia and bacterial infection (54%) (10). Approval of an uridine nucleoside analogue that selectively inhibits HCV NS5B RNA-dependent RNA polymerase (Sofosbuvir) by the FDA late 2013 has led to proof-of-concept trials in which combination all-oral therapy has proven effective for both genotype 1 and other genotypes, with a number of other regimens under development. In particular, the combination of Sofosbuvir (SOF) and Ledipasvir (LDV) has been reported to have almost universal efficacy in a 12 week regimen for genotype 1, and the combination of SOF and Ribavirin (RBV) for genotypes 2-6 in a 24 week regimen (11,12). Most recently, the combination of Sofosbuvir and Velpatasvir (SOF/VEL), Epclusa®, has been shown to have pan-genotypic efficacy in pivotal studies (23,24) and is rapidly becoming standard-of care for chronic HCV infection (25). Inclusion of genotypes 1-6 in our study will allow us to correlate possible confounding factors (e.g. specific extra-hepatic disease manifestations, immunoglobulin V-region gene usage; IL28B genotype; HCV Core gene mutations) compared to the published experience for Sofosbuvir and Velpasvir for other genotypes (23,24). It will also allow us to increase enrollment from a diminishing pool of patients who have yet to undergo treatment with 12 week course of Epclusa® (sofosbuvir/velpatasvir) in compensated patients (Child-Pugh A). In addition, persistence of cryoglobulinemia even after viral clearance with the newer regimens has also raised the question of whether longer treatment regimens may be appropriate in the setting of significant extrahepatic disease (13). To date, only limited published experience exists with regard to the “post-viral” phase of HCV MC, consisting of retrospective analyses involving various genotypes and differing regimens of DAAs (19,26). Thus, the timing is right for a prospective trial of all-oral treatment with Epclusa® (SOF/VEL) to rigorously evaluate the effect on extrahepatic disease manifestations in patients with MC of all genotypes, and to re-establish the efficacy of antiviral therapy in halting the direct and indirect role of HCV in driving autoimmune disease and lymphoproliferation. Using an interferon-sparing regimen to treat patients with HCV-related cryoglobulinemia will help answer the

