## 4. SUBJECT POPULATION

### 4.1. Number of Subjects

Ten patients will be enrolled in this study.

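### The 15% margin of error for 10 patients has no stated SVR rate or interval method behind it, and the design gives that precision only if every patient, or none, reaches SVR

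*Combined protocol and SAP*

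**What the plan says.** Section 4.1 fixes the sample size: "Ten patients will be enrolled in this study". Section 9, repeated in the Synopsis under Statistical Methods, says that with this number the study can "estimate the rate of patients who obtain an SVR with a margin of error of approximately 15" percent. The next sentence plans a "95% confidence interval to describe the rate of SVR in the total sample and the two subgroups of interest".

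Neither place gives an expected SVR rate, names an interval method, or says which confidence level the 15% belongs to. SVR is a primary objective at both 4 and 24 weeks after treatment, and the margin is not tied to either time point.

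Section 1.2 describes expected efficacy only in words. Ledipasvir/sofosbuvir "has been reported to have almost universal efficacy in a 12 week regimen for genotype 1", and sofosbuvir/velpatasvir "has been shown to have pan-genotypic efficacy in pivotal studies". No SVR percentage is attached to either statement.

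**The concern.** The 15% is the only precision figure offered in support of ten patients. For a proportion, the width of the interval depends on the rate and on the method. A single margin with neither stated cannot be checked, and 15 points looks narrow for n = 10.

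The practical risk is misreading. Someone who applies the stated margin to 9/10 gets 75% to 100%. The study's results are also to be compared with published and unpublished experience, so understated uncertainty would carry into that comparison. Because no method is named, a default normal-approximation interval could be used. At 10/10, a plausible result here, it would run from 100% to 100%.

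**Working it through.** **Inputs.** n = 10 (Section 4.1). Stated margin h = 0.15, read as a half-width in percentage points (Section 9). Confidence level 95%, z = 1.96 (Section 9, from the planned intervals). The SVR rate p and the interval method are not given, so the 15% cannot be reproduced forwards. It can only be solved for.

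**1. Rate that gives 15 points.** The normal-approximation half-width is h = z·√(p(1−p)/n). Setting h = 0.15:

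p(1−p) = 10 × (0.15/1.96)² = 0.0586, so p = (1 + √(1 − 4 × 0.0586))/2 = 0.9375.

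The mirror solution, about 6%, is not relevant.

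**2. The same formula at other rates.**

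| Assumed SVR | Half-width (points) |
|---|---|
| 95% | 13.5 |
| 93.75% | 15.0 |
| 90% | 18.6 |
| 80% | 24.8 |
| 50% | 31.0 |

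Other unstated readings also land near 15: 90% confidence with SVR of about 91%, 80% confidence with about 84%, or one standard error at 50% (15.8 points).

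**3. Whether the normal approximation is usable here.** At p = 0.9375, the results whose interval contains p are 7, 8 and 9 out of 10. The interval at 10/10 has zero width, and the one at 6/10 stops at 0.60 + 0.304 = 0.904. Summing the binomial probabilities of 7, 8 and 9 gives a coverage of 0.473 against a nominal 0.95.

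**4. Intervals by observed result (95%, half-width in points in brackets).** Results below 5/10 mirror those above.

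| Result | Normal half-width | Exact (Clopper-Pearson) | Wilson |
|---|---|---|---|
| 10/10 | 0.0 | 69.2–100% (15.4) | 72.2–100% (13.9) |
| 9/10 | 18.6 | 55.5–99.7% (22.1) | 59.6–98.2% (19.3) |
| 8/10 | 24.8 | 44.4–97.5% (26.5) | 49.0–94.3% (22.7) |
| 7/10 | 28.4 | 34.8–93.3% (29.3) | 39.7–89.2% (24.8) |
| 6/10 | 30.4 | 26.2–87.8% (30.8) | 31.3–83.2% (26.0) |
| 5/10 | 31.0 | 18.7–81.3% (31.3) | 23.7–76.3% (26.3) |

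By all three methods, a half-width of about 15 points or less occurs only at 10/10 or 0/10. At 10/10 the exact interval lies wholly below the estimate and reaches 100 − 69.2 = 30.8 points down. Over all results, the farther exact limit is 31 to 36 points from the estimate (Wilson 26 to 31).

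**5. How often the wider intervals would occur.** At p = 0.9375, P(10/10) = 0.9375¹⁰ = 0.5245, so P(9/10 or fewer) = 0.4755. Weighting the exact half-widths by their binomial probabilities gives an expected half-width of 19.2 points. At an illustrative p = 0.97, P(10/10) = 0.737, P(9/10 or fewer) = 0.263 and the expected exact half-width is 17.3 points.

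**6. Subgroups.** Section 9 does not define its two subgroups or give their sizes. If one held 5 patients (an assumption), 5/5 would have an exact lower limit of 0.025^(1/5) = 0.478, an interval of 47.8% to 100% and a half-width of 26.1 points.

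**The case against.** The strongest reply is that 15% is not an arithmetic error. It follows from a 95% normal approximation at 93.75%, and it is close to the exact half-width at 10/10. Both fit the high efficacy described in Section 1.2. The poor coverage and the zero-width interval belong to a method that the plan never names. The half-widths at 50% and 80% describe results far from those expected, and at a true SVR of 97% all ten patients would respond 74% of the time. The quoted sentence makes no claim about subgroups or cryoglobulinemia response. The study is an exploratory pilot with no test, threshold or stopping rule that uses the 15%, and a soundly computed interval will show the real uncertainty whatever the planning sentence says.

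Much of this stands. The 15% is attainable, the defect is an unstated favourable assumption, and the effect on decisions is nil. The subgroup and cryoglobulinemia-response remarks are side points.

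The high-efficacy reading does not rescue the figure, however. The wording about near-universal efficacy concerns ledipasvir/sofosbuvir in genotype 1, whereas patients enrolled under protocol version 2 receive sofosbuvir/velpatasvir for genotypes 1 to 6. Even at 93.75% a result of 9/10 or fewer is nearly as likely as 10/10. At 10/10 itself the exact lower limit is about 31 points below the estimate. The final defence also depends on a sound interval method being used, and the plan does not secure one.

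**Conclusion.** The concern holds. The stated precision cannot be derived from the plan's own inputs and is optimistic for every result except all or none responding. Against a stated 15 points, the exact 95% half-width is 22.1 at 9/10, 26.5 at 8/10 and up to 31.3 at 5/10. Wilson intervals, at 19.3 to 26.3 points for the same mixed results, lead to the same conclusion.

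This rests on reading the margin as a 95% half-width. The plan does not say so, but 95% is the only confidence level it mentions. The consequence is overstated precision in a descriptive pilot, not a wrong decision. It should be corrected because it is the only quantitative support for the sample size and the correction costs almost nothing.

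**What to change.** Keep n = 10. In Section 9 and in the Synopsis, replace the margin-of-error sentence with one along these lines:

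> With 10 patients, the exact (Clopper-Pearson) 95% confidence interval would be 69.2% to 100% if 10 of 10 reach SVR, 55.5% to 99.7% for 9 of 10, 44.4% to 97.5% for 8 of 10 and 26.2% to 87.8% for 6 of 10.

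Name the exact method for all SVR intervals, in the total sample and in the subgroups. Extend it to complete and partial cryoglobulinemia response, a primary objective for which Section 9 plans no interval and gives no precision. Wilson intervals would also serve if preferred, with the example limits changed to match. What matters is that a small-sample method is named.

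The cost is one sentence in two places and a named method. The stated precision becomes less favourable. No patients, visits or procedures are added.
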